8.3.2 DEFINITION OF SERIOUS ADVERSE EVENTS (SAE)

An adverse event (AE) or suspected adverse reaction is considered "serious" if, in the view of either the investigator or sponsor, it results in any of the following outcomes:

- Death
- A life-threatening adverse event
- Inpatient hospitalization or prolongation of existing hospitalization
- A persistent or significant incapacity or substantial disruption of the ability to conduct normal life functions, or
- A congenital anomaly/birth defect

Important medical events that may not result in death, be life-threatening, or require hospitalization may be considered serious when, based upon appropriate medical judgment, they may jeopardize the participant and may require medical or surgical intervention to prevent one of the outcomes listed in this definition. Examples of such medical events include allergic bronchospasm requiring intensive treatment in an emergency room or at home, blood dyscrasias or convulsions that do not result in inpatient hospitalization, or the development of drug dependency or drug abuse.

SAEs will be captured from the time of informed consent until 30 days after the last dose of investigational product. For information on SAE reporting and associated procedures and forms, refer to the study Safety Plan.

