## 4.2 Safety Endpoints

Number of overall adverse events, related adverse reactions, and hospitalizations reported in participants taking 3 g TQ Formula (500 mg per capsule, 3 capsules BID) versus participants

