### 5.2 Analysis Sets

The following are the main analysis datasets defined in the study protocol:

- Full Analysis Dataset: The Full Analysis Set (FAS) is defined as all randomized participants who receive at least one dose of study intervention.
- Final Dataset for Primary Objectives (FDPO): FDPO is defined as all randomized evaluable participants regardless of whether or not they received the assigned treatment regimen according to the evaluability definition above.
- Intent-to-treat (ITT) dataset: ITT dataset is defined as all randomized patients regardless of their adherence to or completion of the study regimen. This dataset includes all randomized participants even if they do not receive any dose or they withdraw from the study without completing the regimen or experience protocol violations.
- Safety Analysis Dataset: The Safety Analysis Set is defined as participants who take at least one dose of study intervention.
- Per-Protocol Analysis Dataset: The Per-Protocol Analysis Set (PP) is defined as all participants in the FAS who complete all visits up to and including Day 14, are compliant with study medication and do not have any major protocol violation. Major protocol violations will be identified prior to breaking the blind.

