# BOSS-Covid-19 Study (BOSS-001)

## 5.3.2 Primary Analyses

Primary estimand-1 is defined to be the difference of median time to sustained clinical response between participants taking 3 g TQ Formula (500 mg per capsule, 3 capsules BID) and participants taking placebo regardless of whether or not they actually receive their assigned therapy (ITT) and assuming that their hospitalization and treatment discontinuation rates will be similar. Possible intercurrent events for this estimand can be, though expected to be quite rare, hospitalization (i.e., transitioning from outpatient status to inpatient status) and treatment discontinuation, both of which may lead to potential missing data or change in the primary measures. The study participants will be reminded to submit their Modified FLU-PRO Plus questionnaires even after these intercurrent events to avoid missing data as much as practically possible. Hospitalization-free, while-on-study and per-protocol treatment versions of the above estimand will also be considered within each population definitions above.

Median time to sustained clinical response for the treatment and placebo arms will be estimated using the Kaplan-Meier method and Log-rank test will be utilized to compare the time to sustained clinical response distributions between the two study arms using LIFETEST procedure in SAS Version 9.4 ® (SAS Institute, Cary, North Carolina, USA). Events will be defined as cases that attain sustained clinical response while on study and time to event will be calculated as the days from the date of symptoms onset to the date that all symptoms are below Level-2 ('A little bit') on the Modified FLU-PRO Plus questionnaire. Patients who do not attain to clinical response while on study will be censored on Day-21 or on the day they are off study before Day-21 due to other reasons.

Although all analyses will be conducted based on the intent-to-treat principle, sensitivity analyses based on the adherence to the protocol regimen will also be carried out for the primary as well as secondary objectives. Sensitivity analyses will also include hospitalization-free, while-on-study, and per-protocol treatment cohorts as described above.

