Primary Estimand-2 for the safety objective is the difference of frequencies of Adverse Events and Serious Adverse Events between participants taking 3 g TQ Formula (500 mg per capsule, 3 capsules BID) and participants taking placebo regardless of whether or not they actually receive their assigned therapy (ITT) and assuming that their hospitalization and treatment discontinuation rates will be similar. The above mentioned intercurrent events are also applicable for this safety estimand. Therefore, hospitalization-free, while-on-study and per-protocol treatment versions of the above estimand will also be considered within each population definitions above.

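### The SAP's primary safety estimand assumes similar hospitalisation rates and adds a hospitalisation-free version, although hospitalisation is part of the safety outcome

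*SAP*

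**What the plan says.** SAP 3.6 lists safety and tolerability as the second primary objective. For it, SAP 5.3.2 sets up Primary Estimand-2, which "is the difference of frequencies of Adverse Events and Serious Adverse Events" between the arms. The comparison is by intention to treat (ITT), whether or not the assigned therapy was received, and is made "assuming that their hospitalization and treatment discontinuation rates will be similar".

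The intercurrent events are carried over from the efficacy estimand, where the SAP writes "Possible intercurrent events for this estimand can be, though expected to be quite rare, hospitalization", followed by treatment discontinuation. For safety it adds: "The above mentioned intercurrent events are also applicable for this safety estimand". It concludes that "hospitalization-free, while-on-study and per-protocol treatment versions of the above estimand will also be considered" within each of the populations defined before.

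Three other places bear on this:

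- SAP 4.2 gives the safety endpoint as "Number of overall adverse events, related adverse reactions, and hospitalizations reported in participants taking" active drug versus placebo.
- Protocol 8.3.2 lists among the SAE criteria "Inpatient hospitalization or prolongation of existing hospitalization".
- SAP 5.2 already has a suitable population: "The Safety Analysis Set is defined as participants who take at least one dose of study intervention". The ITT set in the same section also takes in people who never receive a dose.

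**The concern.** An intercurrent event is something that happens after randomisation and affects the interpretation or existence of the outcome measurements. For time to symptom response, hospitalisation fits that description. For a comparison of SAEs it does not, because it is one of the outcomes. Once hospitalisation is labelled intercurrent, the estimand is stated under an assumption about part of what it should measure, and a version restricted to people never hospitalised becomes a planned result.

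The discontinuation half of the clause has a related weakness. Tolerability is under study, and a poorly tolerated product would be expected to show itself partly through people stopping it.

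The stakes are the final by-arm safety comparison, which carries most of the safety evidence. Protocol 10.1.6 provides for no data and safety monitoring board, and under SAP 7.6 the 12-patient safety review stays blinded unless three or more qualifying cases occur. A hospitalisation-free table presented as a version of the primary safety estimand could be read as reassurance when it has removed the events of most interest.

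**Working it through.** The plan states no figure for this estimand: it has no margin, power or expected rate. The check is therefore a comparison of the texts, followed by an illustration with assumed counts.

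**Step 1: is hospitalisation inside the outcome?** Estimand-2 counts SAEs. Under Protocol 8.3.2 an AE that leads to inpatient hospitalisation is an SAE. Under Protocol 8.3.4 a condition present at screening that deteriorates during the study is recorded as a new AE, so admission for worsening COVID-19 also qualifies. SAP 4.2 counts hospitalisations by name. The answer is yes.

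**Step 2: is discontinuation linked to the outcome?** Protocol 7.2 lists AEs and laboratory abnormalities among the reasons for stopping study treatment, and the dose-modification text in Protocol 4.3 ends in discontinuation for persistent treatment-related toxicity. The answer is again yes.

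**Step 3: what does the hospitalisation-free version do?** For one arm let n be the patients randomised, h those hospitalised with an SAE, and k those with an SAE who were not hospitalised.

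- All randomised: (h + k) / n
- Hospitalisation-free: k / (n − h)

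The count h leaves the numerator entirely, whatever its size. Taking n = 26 or 30 from SAP 3.2 and assuming h and k:

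| Assumed counts (TQ Formula v placebo) | All randomised | Hospitalisation-free |
|---|---|---|
| n = 26; h = 4 v 1; k = 1 v 1 | 5/26 = 19.2% v 2/26 = 7.7%; difference 11.5 points | 1/22 = 4.5% v 1/25 = 4.0%; difference 0.5 points |
| n = 30; h = 4 v 1; k = 1 v 1 | 5/30 = 16.7% v 2/30 = 6.7%; difference 10.0 points | 1/26 = 3.8% v 1/29 = 3.4%; difference 0.4 points |
| n = 26; h = 5 v 0; k = 0 v 0 | 5/26 = 19.2% v 0%; difference 19.2 points | 0% v 0%; difference 0 |

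**Step 4: direction.** Swapping the arms in the first row gives −11.5 points in all randomised and −0.5 hospitalisation-free, so a benefit would be hidden just as a harm would. The restriction can also create a difference. Suppose 8 of 26 patients in each arm have an AE, with none of the 8 hospitalised on TQ Formula and 3 of the 8 hospitalised on placebo. All randomised: 8/26 v 8/26, difference 0. Hospitalisation-free: 8/26 = 30.8% v 5/23 = 21.7%, so TQ Formula looks 9.0 points worse.

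**Step 5: could the trial's own data support the similarity assumption?** Hardly. At 26 per arm Fisher's exact test gives a two-sided p of 0.35 for 4 v 1 hospitalised and 0.051 for 5 v 0. A non-significant result would be no evidence that the rates are similar.

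**Step 6: the per-protocol version.** Protocol 6.4 removes from the per-protocol population anyone missing more than 6 consecutive doses, which at two doses a day is more than 3 days. The same section keeps those patients in the safety analyses. Protocol 4.3 allows toxicity delays of up to 10 days, or 10 × 2 = 20 doses. A patient can therefore be dropped from a per-protocol safety comparison because of the toxicity it is meant to describe.

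**The case against.** The strongest reply is that little depends on the wording. The SAP says similar, not equal, and no test, model or imputation in 5.3.2 or 5.3.6 uses the assumption. The same clause appears in the primary efficacy estimand and in secondary estimands 1 to 3, so it was probably copied. The lead version is the observed ITT difference, which counts hospitalisation SAEs. The hospitalisation-free version is additional, and SAP 5.3.6 and Protocol 9.4.3 tabulate AEs and SAEs by arm without excluding anyone hospitalised. All of this stands. It limits the point, but the assumption and the added version remain in the estimand.

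Three stronger readings are tempting and are not supported:

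- **Hospitalisations vanish from safety reporting.** They do not, for the reasons just given.
- **The restricted versions can only make the arms look alike.** Step 4 shows they can hide a harm, hide a benefit or create a difference.
- **The Safety Analysis Set is never used.** SAP 5.3.2 refers to each population defined before, which can include it. The narrower list under Secondary Aim-1 concerns viral load and contains the Full Analysis Set, in effect the same people. What remains is that the lead population for safety is ITT.

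A reader might also argue that undosed people in the ITT set dilute AE rates by a known amount. The documents do not say how many such people to expect, and AEs are captured from consent, so undosed people can contribute events.

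Finally, a per-protocol AE summary is legitimate if labelled for what it is. Deleting it would be a preference, and is not asked for here.

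**Conclusion.** The point holds in a limited form. Estimand-2 assumes similarity between arms on hospitalisation, which is part of its own outcome, and on discontinuation, which AEs can cause. Its hospitalisation-free version removes every hospitalisation SAE by construction. That rests on the text alone.

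The size cannot be estimated from the documents, which describe hospitalisation only as rare. The fall from 11.5 to 0.5 points is an illustration with assumed counts at 26 per arm. If no one is hospitalised, the hospitalisation-free restriction changes nothing. If every SAE is a hospitalisation, the restricted SAE difference is zero whatever the imbalance.

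The defect lies in the stated assumption and the added version. The lead ITT comparison and the routine safety tables are unaffected. It should be corrected because safety is a primary objective in the SAP and the correction is simple.

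**What to change.** In the Estimand-2 paragraph of SAP 5.3.2:

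1. Delete the clause assuming similar hospitalisation and discontinuation rates.
2. Delete the hospitalisation-free version, and state that hospitalisation is counted as an outcome and is not an intercurrent event for safety.
3. Make the Safety Analysis Set of SAP 5.2 (at least one dose) the lead population.
4. If a per-protocol safety version is kept, label it supplementary and note that it can exclude people who stopped or missed doses because of AEs.

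The existing rule of comparing participants whether or not they received their assigned therapy already covers discontinuation, so no new strategy is needed there. The same wording in the efficacy estimands does not raise this contradiction, because hospitalisation is not part of those outcomes.

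The cost is a SAP wording change before unblinding. It needs no new data and no change to sample size or visits, and it leaves fewer tables to produce.

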# BOSS-Covid-19 Study (BOSS-001)

## 5.3.3 Secondary Analyses

Analysis plan for Secondary Aim-1:

Secondary estimand-1 is defined to be the slope difference of viral load change overtime between participants taking 3 g TQ Formula (500 mg per capsule, 3 capsules BID) and participants taking placebo regardless of whether or not they actually receive their assigned therapy (ITT) and assuming that their hospitalization and treatment discontinuation rates will be similar.

The first secondary endpoint of this clinical trial is the differential change of viral load distribution overtime between the two-study arm. As the viral load will be measured at Baseline, on Day-7, and on Day-14 (and potentially for some patients in Day-4 and Day-10 visits), the outcome variable of interest will be a longitudinal interval-scale measure. To assess the differential behaviour of viral load overtime between the two study arms, Random Coefficients Models will be utilized where viral load will be the dependent variable and study arm and time will be main predictors. Viral load measures may be subjected to some data transformation (e.g., log transformation) to improve the model fit and assumptions as necessitated by model diagnostics. In addressing this objective, all available data will be utilized; that is, in addition to the evaluable patients, data from non-evaluable patients such as data only at baseline visit or data at baseline and Day-10 for example will be used to improve the local fit of the underlying model. To assess differential behavior in total symptom severity score, time\*study-arm interaction will be investigated as well. The above mentioned intercurrent events, namely, hospitalization (i.e., transitioning from outpatient status to inpatient status) and treatment discontinuation, are applicable for Secondary estimand-1 as well. Therefore, hospitalization-free, while-on-study and per-protocol treatment versions of the above estimand will also be considered within each population definitions above, namely, Full Analysis Dataset (FAS), Final Dataset for Primary Objectives (FDPO), and Per-Protocol Analysis Dataset (PPAS). The above analysis will be carried out using the MIXED procedure of SAS software.

Analysis plan for Secondary Aim-2:

Secondary estimand-2 is defined to be the proportion difference of patients with RT-PCR negative/undetectable viral loads between participants taking 3 g TQ Formula (500 mg per capsule, 3 capsules BID) and participants taking placebo regardless of whether or not they actually receive their assigned therapy (ITT) and assuming that their hospitalization and treatment discontinuation rates will be similar. To address this estimand, the percentages of RT-PCR negative/undetectable viral loads between the two study arms will be estimated and compared using Fisher's Exact test at Day-7 and Day-14 visits. The above mentioned intercurrent events for

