9.4.3 ANALYSIS OF THE SECONDARY ENDPOINT(S)

None of the following endpoints depend on the findings of the primary endpoint.

The first secondary endpoint of this clinical trial is the differential change of viral load distribution overtime between the two-study arm. As the viral load will be measured at Baseline, on Day-7, and on Day-14 (and potentially for some patients in Day-4 and Day-10 visits), the outcome variable of interest will be a longitudinal interval-scale measure. To assess the differential behaviour of viral load overtime between the two study arms, Random Coefficients Models will be utilized where viral load will be the dependent variable and study arm and time will be main predictors. Viral load measures may be subjected to some data transformation (e.g., log transformation) to improve the model fit and assumptions as necessitated by model diagnostics. In addressing this objective, all available data will be utilized; that is, in addition to the evaluable patients, data from non-evaluable patients such as data only at baseline visit or data at baseline and Day-10 for example will be used to improve the local fit of the underlying model. To assess differential behavior in total symptom severity score, time*study-arm interaction will be investigated as well.

The percentages of RT-PCR negative/undetectable viral loads between the two study arms will be compared using Fisher's Exact test at Day-7 and Day-14 visits.

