### 7.1 Missing Data and Outliers:

In this study, the primary objective is driven by data collected during the baseline visit and up to Day-21; considering the short treatment and follow-up time, missing data is expected to be minimal. We do not anticipate excessive missing values; however, missingness structure will still be analyzed as to whether or not the missingness is Missing Completely at Random (MCAR), or Missing at Random (MAR), or Not-Missing at Random (NMAR). In the event of MCAR and MAR, sensitivity analyses will be carried out by using Multiple Imputation (MI) techniques when appropriate. Specifically for the Modified FLU-PRO Plus data, Last-Value-Carried-Forward (LVCF) imputation approach will be utilized as this assessment will be for Day-1 through Day-21 and LVCF approach would be appropriate to impute intermittent missing values in these time series type data.

The data quality checks will be an ongoing effort for the study and potential outliers will be detected and resolved as much as possible while the study is ongoing. In the analysis phase, the outliers will be evaluated based on whether or not they are influential values in given statistical model a given outlier may be perfectly in line with the model built and does not necessarily mean problematic for modeling assumptions. If they are found to be influential, then possible data transformation approaches such as log-transformation will be considered.

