## 7.7 Timing with Respect to Database Locking

The data quality checks will be an ongoing effort while the study is still on. When all patients are enrolled and complete their modified Flu-Pro Plus assessment to Day 21, a complete data extraction will be requested for an efficacy data quality control. Once the efficacy data is deemed to be complete and accurate, the efficacy data will be locked and another complete data extraction will be requested to generate a preliminary efficacy report. As part of this preliminary efficacy analysis, the study statistician will be unblinded but all other member of the study team will remain blinded and the preliminary safety report will not contain any individual level data. Upon the completion of the 45-day safety follow-up of the last enrolled patient, there will be a final data quality assessment finalizing the safety parameters, generating final set of queries for the study sites to correct/modify/update. Once all data quality check queries are adequately addressed, the study database will be ordered to be locked and the entire study team will be unblinded to patient randomization.

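### The viral-load slope analysis leaves the scale to be chosen from the trial data and has no rule for undetectable values, so its result depends on a coding choice the plan does not make

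*SAP*

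**What the plan says.** SAP 5.3.3, Secondary Aim-1: "Secondary estimand-1 is defined to be the slope difference of viral load change overtime" between the arms. The model: "Random Coefficients Models will be utilized where viral load will be the dependent variable and study arm and time will be main predictors", run in the SAS MIXED procedure. Protocol 9.4.3 has the same model: "Random Coefficients Models will be utilized where viral load will be the dependent variable". Samples are scheduled at baseline, Day 7 and Day 14.

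The scale is not fixed: "Viral load measures may be subjected to some data transformation (e.g., log transformation) to improve the model fit". A transformation is optional, log is only an example, and the trigger is "to improve the model fit and assumptions as necessitated by model diagnostics". SAP 7.1 adds a second data-driven route, for outliers: "If they are found to be influential, then possible data transformation approaches such as log-transformation will be considered".

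On timing, SAP 7.7 says that for the preliminary efficacy report "the study statistician will be unblinded but all other member of the study team will remain blinded". Neither document requires the scale to be settled before that.

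Undetectable results appear only as a separate binary outcome. Under Secondary Aim-2, "the percentages of RT-PCR negative/undetectable viral loads between the two study arms will be estimated and compared" by Fisher's exact test at Days 7 and 14. Protocol 9.1 (second secondary hypothesis) predicts that the study drug raises that percentage. For the Aim-1 model neither document gives a detection limit, a substitution value or a censored-data method.

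The interaction sentence in the Aim-1 text names the total symptom score instead of viral load.

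**The concern.** A slope in copies per day and a slope in log10 units per day are different quantities, so the estimand is not defined until the scale is chosen. Here the choice may be made by someone who can see the treatment codes.

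The log scale alone does not settle the matter. An undetectable result has no log value until someone assigns one, and MIXED treats whatever is assigned as an exact measurement. With three visits, many patients may be undetectable at the last one, which carries much of the slope information. The plan expects this more often on active, so the censoring would differ between the arms.

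At stake is the first secondary endpoint and the plan's only analysis of quantitative viral load between the arms. An unlucky coding can shrink a real effect. An open choice among codings can also produce a false positive.

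**Working it through.** **No figure to reproduce.** The only power figure in the documents (81.5%) belongs to the primary endpoint. None is given for viral load.

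**Inputs from the documents.** Days 1, 7 and 14; 26 patients per arm (SAP 3.2); two-sided 5% test (Protocol 9.4.1); slope estimand with random coefficients.

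**Inputs assumed, because the documents give none.** Baseline mean B of 5, 6 or 7 log10 (SD 1.5); patient slope SD 0.1 per day; residual SD 0.7; detection limit L of 2 or 3 log10; slopes (placebo / active) of -0.25/-0.35, -0.35/-0.50 or -0.45/-0.65 log10 per day. This makes 3 × 2 × 3 = 18 scenarios, with complete data.

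**Formulas.** At x = 0, 6 or 13 days from baseline, true log10 load is normal with mean m = B + βx and variance s² = 1.5² + (0.1x)² + 0.7². With a = (L - m)/s:
- undetectable fraction = Φ(a)
- mean when undetectables are coded c: E = m(1 - Φ(a)) + sφ(a) + cΦ(a)
- fitted slope = (-6.333·E₀ - 0.333·E₆ + 6.667·E₁₃) / 84.667

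**Central example** (B = 6, slopes -0.35/-0.50, L = 2). At Day 14, s = √(2.25 + 1.69 + 0.49) = 2.105. Placebo: m = 6 - 4.55 = 1.45, Φ(0.26) = 60% undetectable. Active: m = 6 - 6.50 = -0.50, Φ(1.19) = 88%.

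Undetectables set to the limit:
- placebo means 6.004, 4.026, 2.593 give slope -0.261
- active means 6.004, 3.313, 2.121 give slope -0.295
- difference -0.034 against a true -0.150, so 23% is kept

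Undetectables set to 0 log10: slopes -0.354 and -0.431, difference -0.077, so 51% is kept.

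**Mildest example** (B = 7, slopes -0.25/-0.35, L = 2; Day-14 undetectable 20% v 42%). Limit: -0.231 and -0.300, so 69% is kept. Zero: -0.263 and -0.365, so 102% is kept.

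**All 18 scenarios.** Limit substitution keeps 1% to 69% (51% or less in 17 of 18). Half the limit keeps 1% to 74%. Zero coding keeps 3% to 107% by formula; simulation put the top at 108% to 109%. In simulation, comparing mean patient slopes, limit substitution cut power from 80-100% to 5-60%: 99% to 18% in the central example and 80% to 60% in the mildest.

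**Mixed models by maximum likelihood, random intercept and slope** (120 simulated trials each; share of the true difference kept / power). The simulation error on a power near 50% is √(0.25/120), about 5 points.

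| B, slopes, L | No detection limit | Set to limit | Dropped | Left-censored |
|---|---|---|---|---|
| 6, -0.35/-0.50, 2 | 98% / 99% | 24% / 31% | 87% / 82% | 100% / 92% |
| 6, -0.25/-0.35, 3 | 97% / 78% | 34% / 34% | 75% / 47% | 97% / 64% |
| 6, -0.25/-0.35, 2 | 97% / 78% | 52% / 51% | 78% / 57% | 96% / 68% |
| 7, -0.25/-0.35, 2 | 97% / 78% | 69% / 63% | 81% / 68% | 96% / 72% |

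**No true effect** (4,000 simulated trials in each of two scenarios). Four options: log10 with limit substitution, log10 with zero coding, untransformed, and square root. Each alone rejects in 5% or less. At least one rejects in 9.5% and 9.1%.

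**The case against.** The strongest reply is that the damage comes from a rule the plan does not contain. It never says that undetectables are set to the limit, and the results above show that dropping them costs much less and that zero coding sometimes costs nothing. This stands: a reader might infer that the plan biases the slope toward no difference, but the documents do not fix any direction or size.

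Four related points also limit the concern.
- **Raw scale.** Simulated power on untransformed copies is about 1%, and one might take that as the planned analysis. Diagnostics and the outlier clause would probably reject that scale, so it is not a fair estimate of what would happen. What remains is that the choice is data-driven.
- **Growth with effect.** One might say that the loss grows with the drug's effect. The grid moves both arms' slopes together, so it does not isolate that.
- **Aim-2.** A lost slope need not mean a lost antiviral signal, because clearance is tested separately. With 26 per arm, exact Fisher power at Day 14 is 53% in the central example (60% v 88%), 28% in the mildest (20% v 42%), and 0% to 71% over the grid. That protection is real but partial, and it does not correct the slope estimate.
- **Status.** Protocol 9.4.1 calls secondary results hypothesis-generating, without multiplicity control. That lowers the stakes, but a phase 2 estimate of antiviral effect still informs what is done next.

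**Conclusion.** The concern holds as a gap in specification with a material consequence. The scale may be chosen from the data, possibly after unblinding, and the Aim-1 model has no treatment for values that the plan expects and predicts will differ between arms.

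Its size cannot be derived from the documents. Under the stated assumptions the share of the true slope difference that survives is 1-69% with limit substitution, 75-87% with undetectables dropped (four scenarios) and 3% to about 110% with zero coding. Picking the best of four options gives about 9% type I error. The loss is large when most patients are undetectable by Day 14 and modest when few are.

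A left-censored log10 model with random slopes recovered 96-100% of the difference, with power 64-92%, against 31-63% for limit substitution in the same four scenarios. In the mildest one the gain (72% v 63%) is small relative to simulation error.

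Linear time is implied by the word slope rather than stated. The primary endpoint and the sample size are not affected. This should be corrected, but it does not threaten the trial's main result.

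**What to change.** Before any unblinding, replace the transformation sentence in SAP 5.3.3 Aim-1 with text to this effect:

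> Viral load will be analysed on the log10 scale in the assay's reported quantitative unit. Values below the assay limit, which will be stated, will be treated as left-censored at that limit in a mixed-effects (Tobit) model with arm, time and arm-by-time and random intercept and slope (SAS PROC NLMIXED).

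The random slope should stay. A censored model with only a random intercept, simulated under no effect with patient slope SD 0.1 to 0.15, rejected in about 9% to 13% of 300 trials. The unit is left to the assay because neither document states it.

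Keep the limit-substituted MIXED fit as a sensitivity analysis, and amend SAP 7.4, which now says that sensitivity analysis does not apply. Correct the Aim-1 interaction sentence so that it names viral load.

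A Day-7 change contrast is an optional supportive result, since Protocol 4.1 states a Day-7 hypothesis. Under limit substitution it kept 75% to 96% of the true Day-7 difference in the five scenarios run.

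The cost is one SAP paragraph and one program, with no change to trial conduct. The price is slightly more programming, a distributional assumption below the limit, and possible convergence difficulty with three visits per patient.
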